5.2 Secondary aims

- To correlate the degree of liver fat infiltration and liver stiffness using MR Elastography
- To investigate the hypothesis of a linear correlation between adrenal gland size and variables commonly associated to insulin resistance such as BMI, visceral fat and liver steatosis.

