7 SUBJECT SELECTION

7.1 Study population

Obese patients of either sex with BMI over 30 kg/m², who agree to participate in the study.

7.2 Inclusion criteria:

- Patients of either sex, older than 18 years
-

-
- Obese patients with BMI equal or over 30kg/m²
 - Patients who agree to participate and sign the Informed Consent

7.3 Exclusion criteria:

- Pregnant or lactating women.
 - Patients weighing over 140 kg (by limitation of the MRI device)
 - Patients on anti-obesity drugs (eg, sibutramine, orlistat and liraglutide) or weight-interfering medications (eg, topiramate). In such cases a wash out period of 3 months is required.
 - Patients with alcohol intake > 20 g/day in women and > 30 g/day in men.
 - Patients with liver failure or with pathologies that may affect the liver
 - Patients with other causes of liver steatosis: chronic viral hepatitis and/or drug intake (corticosteroids, estrogens, NSAIDs, calcium antagonists, amiodarone, tamoxifen, tetracyclines, chloroquine, antiretrovirals, perhexiline).
 - Patients with eating disorders.
 - Patients with any psychiatric disorder (eg schizophrenia, bipolar disorder, substance abuse, severe depression).
 - Patients receiving dicumarinic anticoagulants (Sintrom®).
 - Patients taking corticosteroids.
 - Patients with severe kidney failure (gfr <30).
 - Patients with type 1 and type 2 diabetes mellitus.
 - Patients with hemopathies, including coagulation disorders
 - Patients with cardiovascular or cerebrovascular disease (of heart rate disorders, recent infarction [$<6m$], unstable angina, decompensated heart failure, recent stroke [$<6m$]).
 - Patients in acute attack of gout.
 - Patients with renal lithiasis verified by ultrasound.
 - Patients with cholelithiasis verified by ultrasound.
 - Patients with electrolyte imbalance, according to medical criteria.
 - Patients with orthostatic hypotension.
 - Patients with cancer or history of cancer who have not been discharged from oncology
 - Patients who are not expected to attend follow-up visits
-

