9 STUDY PROCEDURES AND OUTCOME MEASURES

9.1 Outcome measures

9.1.1 *Primary variables*

- Liver fatty infiltration, measured by a MRI technique of fat liver quantification (Ideal IQ**).
- Visceral fat, measured by the area in squared centimeters at the level of the 3rd vertebrae, using MRI technique.

9.1.2 *Secondary variable*

- Liver stiffness detected by MR Elastography
- Adrenal gland linear measurement
- Body weight
- Salivary cortisol levels

9.1.3 *End points*

- Reduction of fat infiltration into the liver between the baseline visit and 2 months (or end of the ketosis stage) and between the baseline visit and the control visit at month 6 of treatment.
- Visceral fat reduction between the baseline visit and 2 months (or end of the ketosis stage) and between the baseline visit and the control visit at month 6 of treatment.
- Correlation between degree of liver fat infiltration and liver stiffness
- Correlation between adrenal gland size and BMI, visceral fat and liver steatosis.
- Correlation between salivary cortisol levels and BMI, visceral fat and liver steatosis.
- Weight loss between the baseline visit and 2 months (or end of the ketosis stage) and between the baseline visit and the control visit at month 6 of treatment.

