9.2 Study procedures

9.2.1 *Follow-up of patients*

The patient follow-up will be 6 months. The patients will be visited monthly and data will be recorded on 4 occasions: pre-inclusion, baseline visit, final visit Active stage (end of ketosis) and visit at month 6.

Patients will be included after verifying the inclusion and exclusion criteria and after obtaining the signed informed consent.

Screening visit (day -15). In this visit, the patient's medical history will be assessed and a complete blood test will be required to verify the inclusion/exclusion criteria: complete blood count (red blood cells, leukocytes, neutrophils, hematocrit, hemoglobin), fasting blood glucose, Hb1c, insulinemia, lipid profile (total cholesterol, c-HDL, c-LDL, triglycerides), kidney function (serum creatinine, creatinine clearance, glomerular filtration), nitrogen balance (urea, uric acid), thyroid profile (TSH, T4) and ionogram (Na, K, Cl, Ca, Mg)

The pre-inclusion blood test will also include liver function tests as the first screening of hepatic steatosis:

- GOT
- GPT
- Gamma-GT
- Bilirubin
- Albumin
- Prothrombin time
- Ferritin
- Alkaline phosphatase.

In addition, the patients will be informed about the study through the patient information sheet (Attachment 1) and they will be provided with an informed consent (Attachment 2).

At the baseline visit (day 0). The results of the additional tests (blood tests) will be verified to complete the inclusion/exclusion criteria.

Liver function data will be reviewed. Patients with one or more of the following conditions will be considered as suspicious of hepatic steatosis:

- GPT/GOT ratio over 1
- Gamma-GT and alkaline phosphatase increased twice to three times the normal levels
- High ferritin
- Normal bilirubin and albumin in the presence of any of the above changes

The informed consent will be signed and randomized. The corresponding diet will be scheduled depending on the treatment group (VLCK diet group or control group) and the physical exercise program. Patient demographics (sex, age, weight, height, comorbidities and medication) will be recorded. Anthropometric data (weight, BMI, waist circumference) will be recorded. Fat infiltration into liver and visceral fat will be scanned by MRI and hepatic stiffness will be assessed by MR Elastography. The salivary cortisol levels will also be tested.

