10.2 Analysis of objectives

For the analysis of the primary objective and the secondary objectives, the differences between visits and between groups will be studied for the changes in the ratio between liver fat and the degree of steatosis (measured by MRI), changes in the degree of liver stiffness, changes in cortisol levels in saliva, weight changes, BMI and waist circumference, and changes in the amount of visceral fat among visits. The qualitative variables will be compared using Fisher's exact test, and the quantitative variables will be compared by means of the Student's t test for paired data. If the conditions to apply the Student's t test are not met, we will use the non-parametric Mann-Whitney U test. In the case of comparing paired data, we will use the tests described above, in their version for comparing this type of data.

The Pearson correlation coefficient or Spearman's correlation coefficient if the application conditions are not met will be used to study the following: the association between reduction of hepatic steatosis and weight loss and loss of visceral fat; the association between hepatic steatosis and liver stiffness; and the association between adrenal gland size and salivary cortisol levels with weight changes, BMI, hepatic steatosis and visceral fat.

For all tests, the significance level will be set at $p < 0.05$.

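### Section 10.2 tests the adrenal-size hypothesis only with crude correlations in a mixed-sex sample; where both variables differ by sex or stature, the coefficient can reflect sex or body size

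*Combined protocol and SAP*

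**What the plan says.** Section 5.2 states a hypothesis as a secondary aim: "To investigate the hypothesis of a linear correlation between adrenal gland size and variables commonly associated to insulin resistance", naming BMI, visceral fat and liver steatosis. Section 9.1.3 adds a cortisol counterpart: "Correlation between salivary cortisol levels and BMI, visceral fat and liver steatosis".

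Section 10.2 gives the method: "The Pearson correlation coefficient or Spearman's correlation coefficient if the application conditions are not met will be used to study the following". The list that follows includes "the association between adrenal gland size and salivary cortisol levels with weight changes, BMI, hepatic steatosis and visceral fat". No covariate, partial correlation, regression model or stratification is named. The section does not say which visit supplies the data or, apart from weight, whether levels or changes are correlated. The significance level is 0.05 for all tests.

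Eligibility in section 7.2 covers "Patients of either sex, older than 18 years" with a BMI of at least 30 kg/m², and no sex quota. Section 7.3 excludes anyone above 140 kg because of the scanner. Section 9.1 takes adrenal size as a linear measurement and visceral fat as an area in cm², neither scaled to body size. Section 9.2.1 says of the baseline visit: "Patient demographics (sex, age, weight, height, comorbidities and medication) will be recorded". Sex, age and height are thus available, but section 10.2 does not use them for these associations. Sections 7.4 and 7.5 set 40 patients in an exploratory pilot, with no power calculation.

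**The concern.** These correlations relate measured characteristics to one another across patients. They do not compare randomised arms, so the 1:1 allocation in section 6.2 gives no protection against confounding by sex or stature. If men have both larger adrenals and more visceral fat than women, pooling the sexes produces a positive coefficient even when the two are unrelated among men and among women. A significant result could then be taken as support for the insulin-resistance hypothesis when it only separates men from women. If the sex differences run in opposite directions, a real association can be missed. What is at stake is the interpretation of a stated secondary aim; no primary endpoint is involved.

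**Working it through.** **Inputs from the documents.** n = 40 (section 7.4); alpha = 0.05 (section 10.2; two-sided assumed, as sidedness is not stated); weight limit 140 kg (section 7.3). The plan gives no power, effect size or SD, so there is no figure of its own to reproduce. With n = 40 the crude correlation has 38 degrees of freedom, and |r| must exceed 0.312 to be significant.

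**Assumed inputs.** The documents give neither the share of men nor any sex difference. I take 12 to 20 men (p = 0.3 to 0.5) and male–female differences d1 and d2, in within-sex SDs, over a range.

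**Step 1: correlation produced by sex alone.** With no association within sex,

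r = p(1−p)·d1·d2 / √[(1 + p(1−p)·d1²)(1 + p(1−p)·d2²)].

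Example with p = 0.5 and d1 = d2 = 1: 0.25 / 1.25 = 0.20. With d1 = d2 = 1.5: 0.5625 / 1.5625 = 0.36. Rejection rates come from simulated samples of 40, at least 20,000 per scenario; separate runs differ by about one percentage point.

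| Difference in both variables | r, 12 men | False positives, 12 men | r, 20 men | False positives, 20 men |
|---|---|---|---|---|
| 0.5 SD | 0.05 | 6% | 0.06 | 6% |
| 0.8 SD | 0.12 | 11% | 0.14 | 14% |
| 1.0 SD | 0.17 | 19% | 0.20 | 24–25% |
| 1.5 SD | 0.32 | 56% | 0.36 | 67–68% |

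**Step 2: unequal differences.** The product d1·d2 drives the result, so one small difference nearly removes it. With p = 0.5, d1 = 1.5 and d2 = 0.3: 0.1125 / √(1.5625 × 1.0225) = 0.09. Across 1.0–1.5 SD in one variable and 0.3 SD in the other, false positives are 6–9%. If only one variable differs, r = 0 and the rate is 5%.

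**Step 3: masking.** With a true within-sex correlation of 0.45, the numerator becomes 0.45 + p(1−p)·d1·d2. With 20 men:

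- d1 = −0.5, d2 = 0.8: r = 0.35 / √(1.0625 × 1.16) = 0.31, and power falls from 85% to 51%.
- d1 = −0.8, d2 = 0.8: r = 0.29 / 1.16 = 0.25, and power falls to 33%.

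**Step 4: the weight limit.** The highest BMI that can be enrolled is 140 / height²: 54.7 at 1.60 m, 48.4 at 1.70 m, 43.2 at 1.80 m and 38.8 at 1.90 m. To gauge the effect, assume mean heights of 1.75 m and 1.62 m (SD 0.07 m), a mean BMI of 35–40 before the limit, and adrenal size rising about 1 SD per 10 cm of height. The limit alone then induces an adrenal–BMI correlation of −0.04 to −0.14, well inside ±0.312. Under the same assumptions it lowers a true crude adrenal–BMI correlation of about 0.34 to 0.10–0.29.

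**Step 5: adjustment.** Partialling out sex, age and height leaves 35 degrees of freedom and a critical |r| of 0.325. Simulated false positives are 4.9–5.2% in every scenario. Power for a within-sex r of 0.45 is about 82%, including in the masking scenarios.

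**The case against.** The strongest reply is that the size is assumed. No document gives a sex difference for adrenal size, visceral fat, steatosis, BMI or cortisol, and the high rates need large differences in both variables at once. This stands: a reader might infer that the crude test has a false-positive rate of 11% to 67%, and the documents do not support that as a property of this trial.

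Second, one figure should not be spread over every pair. A reader might extend the point to cortisol and to changes over time. For cortisol it applies only if cortisol itself varies with sex or height. If changes are correlated, fixed differences in level cancel, and bias remains only if the changes differ by sex or height. Section 10.2 lists weight changes among the correlates and does not fix the visit, so this limit is real. Pooling two diets could also create correlations between changes, which is a separate matter that adjustment for sex and height would not remove.

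Third, a reader might infer that the 140 kg limit by itself produces or hides the association. Alone it induces only a small negative coefficient. It could weaken a true BMI association, but that rests on assumed heights and BMI spread. It is a minor further reason to include height, and nothing here bears on the eligibility rule.

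Fourth, these are secondary aims in an exploratory pilot, and a crude coefficient directly estimates the linear correlation that section 5.2 names. That is a good reason to keep the crude coefficients. It does not make them sufficient: the aim ties the correlation to insulin resistance, section 10.2 tests it at p < 0.05, and section 13.2 foresees publication.

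**Conclusion.** The point holds in a conditional form. The documents establish that only crude coefficients are planned, that both sexes are enrolled, that adrenal size is not scaled to body size, and that recorded sex and height go unused in these associations. It follows that a crude coefficient of levels can reflect sex or stature whenever both variables differ by them. The inflation is negligible when both differ by about 0.5 SD or less, or when either differs little, and becomes material from about 0.8 SD in both. Which case applies cannot be told from the documents. The point is strongest for adrenal size against visceral fat, BMI and steatosis. It concerns the interpretation of a secondary aim and leaves the primary endpoints untouched.

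**What to change.** In section 10.2, for the cross-sectional associations of adrenal size (and of cortisol) with visceral fat, BMI and steatosis, add partial correlations or linear models adjusted for sex and height, with age optional. State which visit supplies the data. Report the adjusted estimates with 95% confidence intervals beside the crude coefficients, and say in advance that the insulin-resistance hypothesis will be interpreted from the adjusted estimate.

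The cost is wording only, since sex, age and height are already recorded at baseline. It uses two degrees of freedom of 38, or three with age, and power for a within-sex correlation of 0.45 becomes about 82% instead of 85%. Separate analyses by sex would be a poor substitute: with 20 patients per sex the critical |r| is 0.444, and 80% power needs r of about 0.59.

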10 STATISTICAL ANALYSIS

10.1 Descriptive statistics

A descriptive statistics will include all variables collected in the Data Collection Notebook. Frequency tables will include the nominal variables and measures of central tendency and dispersion for the continuous variables. 95% confidence intervals (95% CI) will be estimated for the latter.

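### Two primary variables over two intervals are tested at 0.05 both between visits and between groups, and no single contrast is named to answer the primary aim

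*Combined protocol and SAP*

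**What the plan says.** Section 9.1.1 lists two primary variables with equal standing: "Liver fatty infiltration, measured by a MRI technique of fat liver quantification (Ideal IQ") and "Visceral fat, measured by the area in squared centimeters at the level of the 3rd vertebrae, using MRI technique". Section 9.1.3 gives each of them two intervals. For liver fat the first is "Reduction of fat infiltration into the liver between the baseline visit and 2 months (or end of the ketosis stage"), and for visceral fat "Visceral fat reduction between the baseline visit and 2 months (or end of the ketosis stage"); the second for both is baseline to month 6. Section 5.1 puts both variables into a single primary aim.

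Section 10.2 says that "the differences between visits and between groups will be studied" for these and several other variables, that "the quantitative variables will be compared by means of the Student's t test for paired data", and then: "For all tests, the significance level will be set at" p < 0.05. It gives no testing order, no adjustment and no rule on whether one or both variables must succeed.

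On interval estimates, Section 10.1 says of the continuous variables that "95% confidence intervals (95% CI) will be estimated for the latter". Section 10.2 mentions no interval for a difference between arms.

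Sections 1.1, 1.3 and 6.1 call the study a pilot, and Section 7.5 calls it exploratory. The sample is 20 per arm (Section 7.4), with no effect size, standard deviation or power behind it.

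**The concern.** A plan that labels variables as primary and tests them for significance should say in advance which result settles the primary aim. This one leaves three choices open: which variable, which interval, and whether a change within an arm or a difference between arms decides. Any one of four between-arm results could later be presented as the primary finding. So could a before-after result. Both arms receive a weight-loss diet, so a significant fall in liver fat within the ketogenic arm would say little about whether that diet does better than the control diet.

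The choice of interval also changes the question. The month-2 contrast concerns the ketogenic stage. The month-6 contrast concerns the whole programme, after the four-month food re-education stage (Section 8.1). With both primary and neither named, the data can choose between the two questions.

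**Working it through.** **Inputs.** Two primary variables (9.1.1); two intervals for each (9.1.3); 0.05 per test (10.2); 20 patients per arm (7.4). Sidedness is not stated; two-sided tests are assumed. The correlations between contrasts are not given and are varied below.

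**The plan's own figure.** There is none to reproduce. The 0.05 is a per-test level, no overall error rate is stated, and the sample size is not derived from anything.

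**Count.** Between-arm primary contrasts: 2 variables × 2 intervals = 4. Before-after tests in each arm would add 4 × 2 = 8. Those test a different null hypothesis (no change over time), so they are left out of the error rate.

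**Independent tests.** If there is no true difference on any contrast and any one significant result counts as success:

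1 − 0.95⁴ = 1 − 0.8145 = 0.1855, or 18.5%.

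**Correlated tests.** Positive correlation lowers this figure. Two structures were simulated. The first is four two-sample t tests with 20 per arm, 100,000 trials per setting, with correlation r between intervals and r between variables (so r² between different variables at different intervals). The second is four normal statistics with every pair correlated at r.

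| Assumed r | r between intervals and between variables | r for every pair |
|---|---|---|
| 0.3 | 17.6% | about 17% |
| 0.5 | 16.3% | about 16% |
| 0.7 | 13.8% | about 13% |
| 0.9 | 9.9% | about 9% |

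With unequal correlations in the first structure, 0.8 between intervals and 0.5 between variables gives 14.2%; 0.9 and 0.5 gives 12.7%. The rate reaches 5% only if the four tests are perfectly correlated.

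**Effect of naming a contrast.** One variable, one interval, between arms: 5%. Naming only the variable or only the interval leaves two tests: 1 − 0.95² = 9.75% if independent. Keeping all four at 0.05/4 = 0.0125 gives 1 − 0.9875⁴ = 4.9% if independent.

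**Precision.** Half-width of a 95% interval for a between-arm difference with all 40 patients evaluable:

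t(0.975, 38) × √(2/20) = 2.024 × 0.316 = 0.64 SD.

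The interval therefore spans about 1.28 SD in all, and more if patients are lost.

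**The case against.** The strongest reply is that this is an exploratory pilot. It states no confirmatory hypothesis, power target or overall error rate, so 5% familywise is a standard it never set itself. That stands. A reader might infer that the plan breaks a 5% guarantee; the documents do not support that.

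The error rates also depend on a success rule that the plan does not contain. If both variables had to succeed at one named interval, there would be no inflation. This stands too, and the figures are conditional on the any-one-of-four reading. Nor is 13% a floor: the changes in one variable share a baseline, and the primary aim ties both variables to weight loss, so high correlation is plausible.

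A reader might also infer that the between-arm result will be reported only as p-values. Section 10.2 does not say so. The gap is narrower: an interval for the between-arm difference is not explicitly promised.

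On the test, Section 10.2 gives the Mann-Whitney test as the fallback and then mentions paired versions separately, so the word paired in the main sentence may be a slip. Even so, the sentence as written does not specify a between-arm test.

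Finally, the choice of contrast can be disputed. Section 5.1 names visceral fat first, and month 2 isolates the ketogenic stage. That is a reason to let the sponsor justify its choice, not a reason to make none. The pilot label does not remove the need: the plan still designates primary variables and tests them, and Section 13.2 looks ahead to publication. Fixing one comparison in advance requires no alpha adjustment and is compatible with a pilot.

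**Conclusion.** The concern holds as a lack of specification. Sections 9.1.1, 9.1.3 and 10.2 leave four between-arm contrasts, plus before-after tests, any of which could be put forward as the primary result. No error guarantee is broken, because none is claimed.

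The size is up to 18.5%, falling to about 13–14% at an assumed correlation of 0.7 and 9–10% at 0.9. These figures rest on three assumptions: no true difference on any contrast, any one significant result being read as success, and correlations that the documents do not give. They show how far an unplanned choice could mislead; they are not the trial's error rate. The 0.64 SD half-width assumes complete data.

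This is worth correcting before analysis because it is cheap. It does not invalidate the design.

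**What to change.** Before analysis, name one between-arm comparison as primary and carry it through Sections 5.1, 9.1.1, 9.1.3 and 10.2. Editing only some of these would leave visceral fat primary elsewhere and create a new contradiction.

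- **Contrast.** The between-arm difference in change in MRI liver fat from baseline to month 6 is a reasonable default. It matches the condition under study (Section 1.10). Month 6 is also a common time point, whereas under Section 9.2.1 the end-of-ketosis scan may come before month 2 in the ketogenic arm only. The sponsor may justify another choice.
- **Measure and test.** Use the MRI liver fat of Section 9.1.1. Section 10.2 instead describes a ratio of liver fat to steatosis grade and should be aligned. Specify an independent-groups test for the between-arm comparison, not the paired t test.
- **Other contrasts.** Report the remaining three as secondary between-arm estimates with 95% confidence intervals and no claim of significance. Label within-arm before-after tests descriptive.
- **Intervals.** State in Sections 10.1 and 10.2 that 95% confidence intervals will be given for all between-arm differences.

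This needs no extra patients, visits or scans, but it has two costs. Three of the four contrasts lose primary status. With a month-6 primary, patients whose only follow-up scan is at the end of ketosis would lack the primary outcome, although they are not dropouts on the MRI criterion of Section 7.7. The plan must say how they will be handled.
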